PROTOCOL SUMMARY

Evaluating Alternative Medical Therapies in Primary Hyperparathyroidism

NCT02525796

2/2/2021

**AIM:** To conduct a double-blinded, placebo-controlled, randomized intervention study to investigate whether mineralocorticoid receptor (MR) antagonism, alone or in combination with cinacalcet, is an effective therapy for primary hyperparathyroidism (P-HPTH).

- Hypothesis: The aim will test the hypothesis that MR antagonism is a mechanism to lower parathyroid hormone (PTH) in primary hyperparathyroidism (P-HPTH).
- Study Design: Sixty subjects with P-HPTH will be enrolled to randomly receive eplerenone (a potassium-sparing diuretic that directly blocks the MR), amiloride (a potassium-sparing diuretic that *does not* directly block the MR), or placebo for 4 weeks +/- 3 days. Thereafter, *all* subjects will receive cinacalcet therapy (a calcimimetic that lowers PTH) *in addition* to their randomized intervention for an additional 2 weeks +/- 3 days.
- Anticipated Results: In this novel proof-of-concept study, eplerenone therapy will lower PTH, serum calcium, and markers of bone resorption in P-HPTH, when compared to placebo. The PTH response to amiloride will resemble that of placebo, suggesting that the eplerenone mediated reductions in PTH are specific to interactions with the MR. Combination therapy with eplerenone + cinacalcet will result in additive or synergistic reductions in PTH, when compared to placebo + cinacalcet or placebo + amiloride.
- Implications: MR antagonism (alone or in combination with cinacalcet) may be a mechanism to lower PTH and calcium in P-HPTH, thereby identifying a new potential option in the limited medical therapies for P-HPTH.

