Following a safety visit at t=2 weeks +/-3 days (see details of safety visits below), the blinded study drug may increase from the initial dose if the PI perceives the risk for hypotension to be low and as long as all safety parameters are fulfilled. The maximum dose any subject may receive is (EPL 50mg BID, amiloride 5 mg BID, placebo 1 dose BID). If the safety parameters are not within normal limits, the safety check will be repeated within 5 days and the dose may be reduced. At t=4 weeks +/- 3 days, subjects will return to the Clinical Research Center to assess outcome variables (**Figure, visit B**). Following visit B, all subjects will receive open-label cinacalcet **in addition** to continuing their blinded study drug. The initial dose of cinacalcet will be dictated by the subject's serum calcium levels and the PI's clinical judgment as it relates to reasonable safety. The initial doses of cinacalcet will range from 15 mg/d to 15 mg BID. Generally, if the subject is hypercalcemic, the initial dose will be 15mg BID, and if they are normocalcemic the dose will be 15 mg/d; however, the PI may alter this if other clinical factors indicate a more judicious approach for safety (i.e. preventing hypocalcemia). Following another safety visit 1 week +/- 3 days after cinacalcet initiation, cinacalcet may be increased to a maximum dose of 30 mg BID. If the serum calcium levels have normalized to within reference

range, it will be at the PI's discretion to increase the dose of cinacalcet, or maintain the same dose, based on the perceived risk of hypocalcemia. If the safety parameters are not within normal limits, the safety check will be repeated within 5 days and the cinacalcet dose may be reduced. Cinacalcet acts as a calcimimetic by allosteric activation of the calcium-sensing receptor and thereby decreases PTH. Cinacalcet administration to subjects with P-HPT will lower PTH and calcium, and will serve to evaluate whether the combination of EPL+cinacalcet can induce additive or synergistic reductions in PTH, when compared to those induced by placebo+cinacalcet (see *Anticipated Results*). Subjects who are instructed to increase their dose following the safety check will be told to take the blinded study drug and cinacalcet everyday at 8AM and 8PM. Subjects will return after 2 weeks +/- 3 days of cinacalcet therapy for the final study visit (**Figure, visit C**).

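### Exploratory Outcome 2 cannot show synergy, or additivity at a common cinacalcet dose, because cinacalcet dose follows calcium after randomization and every arm receives it

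*Protocol*

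**What the plan says.** **Cinacalcet dosing** (Protocol, Study Procedures, Study Drug Interventions). Following visit B, after about 4 weeks of blinded drug, "all subjects will receive open-label cinacalcet" on top of that drug.

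- Starting dose: "The initial dose of cinacalcet will be dictated by the subject's serum calcium levels and the PI's clinical judgment". The general rule is "Generally, if the subject is hypercalcemic, the initial dose will be 15mg BID, and if they are normocalcemic the dose will be 15 mg/d", which the PI may alter for safety.
- Titration: after a further safety visit about a week later, "cinacalcet may be increased to a maximum dose of 30 mg BID". Where calcium has normalized, "it will be at the PI's discretion to increase the dose of cinacalcet, or maintain the same dose".

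**Purpose of this phase.** The same section says it will show whether EPL plus cinacalcet "can induce additive or synergistic reductions in PTH, when compared to those induced by placebo+cinacalcet". The Protocol Summary (Anticipated Results) gives the comparators differently: "when compared to placebo + cinacalcet or placebo + amiloride".

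**Expected effect on calcium.** Anticipated Results states that "eplerenone therapy will lower PTH, serum calcium, and markers of bone resorption in P-HPTH, when compared to placebo". The SAP's Statistical Plan uses a calcium change of -0.20 to -0.32 mg/dL against 0 on placebo. Study Drug Interventions also expects EPL to reduce urinary calcium excretion.

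**Status of the outcome.** The Protocol's Sample Size section lists the PTH response to EPL plus cinacalcet as Exploratory Outcome 2 and labels it as visits A to B. The SAP's Statistical Plan gives no contrast, dose summary or power for it.

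**The concern.** The variable that guides cinacalcet dose is one the randomized drug is expected to move. If EPL lowers calcium, more EPL subjects will be normocalcemic when cinacalcet starts and will begin on half the daily dose (15 rather than 30 mg). Titration, again guided by calcium, can then spread doses from 15 to 60 mg/d. The arms would be compared at different amounts of the second drug.

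Separately, no arm continues on EPL alone or placebo alone from B to C. Blinded drug may have been raised as late as the week 2 safety visit, so EPL may still be exerting additional effect after visit B. That effect would look the same as an interaction with cinacalcet.

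At stake is the reading of this exploratory outcome. A truly additive combination could look less than additive, a null could be taken as no added benefit, and an apparent excess could be called synergy without support.

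**Working it through.** **1. The plan's own figures.** A two-sample t-test (noncentral t, two-sided alpha 0.05, difference 9.0 pg/mL, SD 9.4) has 79.7% power at 18 per arm and 81.9% at 19. The SAP's 19 is reproduced, as is its 24 for 90% power. A three-arm one-way ANOVA reproduces both calcium rows (17 and 22; 8 and 10) with SD 0.21. These figures are sound, but they concern change from A to B. The SD of 0.21 is for the change in calcium; it does not say where subjects lie relative to the upper reference limit.

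**2. What the B-to-C contrast contains.** Let f(D) be the PTH change produced by cinacalcet dose D (negative), h the further effect of EPL after visit B, and I the interaction. Then:

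- EPL arm: h + mean f(D_EPL) + I
- Placebo arm: mean f(D_placebo)
- Difference: h + [mean f(D_EPL) - mean f(D_placebo)] + I

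There are three unknowns in one observed difference. Concluding I < 0 (synergy) or I = 0 (additivity) requires h to be zero or known and the bracket to be zero or known. The design fixes neither. The A-to-C difference adds the A-to-B effect to the same sum. As a total it is a properly randomized quantity, but it does not isolate I.

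**3. How large the dose imbalance could be (illustration).** The documents give no mean and no between-subject SD of calcium. Assume that calcium at the start of cinacalcet is normal on placebo, with mean c above the limit and SD s, and that EPL shifts it down by d. The extra share of EPL subjects who are normocalcemic is

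Gap = Phi((d - c)/s) - Phi(-c/s).

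Inputs: d = 0.20 to 0.32 mg/dL (SAP); c = 0 to 0.8 and s = 0.3 to 0.8 mg/dL (both assumed).

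| c | s | Gap, d = 0.20 | Gap, d = 0.32 |
|---|---|---|---|
| 0 | 0.3 | 24.8 points | 35.7 points |
| 0.16 | 0.3 | 25.6 | 40.6 |
| 0.4 | 0.5 | 13.3 | 22.5 |
| 0.8 | 0.3 | 1.9 | 5.1 |
| 0.8 | 0.8 | 6.8 | 11.6 |

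- Largest: c = 0.16, s = 0.3, d = 0.32 gives Phi(0.533) - Phi(-0.533) = 0.703 - 0.297 = 0.406.
- Smallest: c = 0.8, s = 0.3, d = 0.20 gives Phi(-2.00) - Phi(-2.67) = 0.0228 - 0.0038 = 0.019.

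So the gap runs from about 2 to 41 points, or about 0.4 to 8 of 20 subjects. The difference in mean starting dose is 15 mg/d times the gap, 0.3 to 6.1 mg/d.

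The normal shape is not essential. Under a uniform shift the gap is simply the share of the placebo distribution lying within d above the limit. The Inclusion Criteria admit subjects above the limit or within 0.2 mg/dL of it, so some subjects in that band are plausible.

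**4. Effect on PTH.** Assume the higher starting dose lowers PTH by an extra 3 to 9 pg/mL (not in the documents). The bracket in step 2 is then gap times that amount. Gaps of 10 to 30 points give 0.3 to 2.7 pg/mL; the full range gives about 0.06 (0.019 x 3) to 3.7 (0.406 x 9). For example, a 20-point gap and 6 pg/mL, with h = 0 and I = 0, makes an additive combination look 1.2 pg/mL worse than additive. If EPL raised calcium, the sign would reverse. Titration is not modelled.

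**5. Precision.** If SD 9.4 also held for the B-to-C change (assumed), the standard error at 20 per arm would be 9.4 x sqrt(2/20) = 2.97 pg/mL. The smallest difference detectable with 80% power would be 8.5 pg/mL, and power for 4.5 pg/mL would be 31%.

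**6. Two text conflicts.** The Sample Size section places Exploratory Outcome 2 at visits A to B, but cinacalcet starts only after B. Anticipated Results names placebo + amiloride as a comparator. No such group exists: after B the groups are EPL, amiloride or placebo, each with cinacalcet.

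**The case against.** The strongest reply is that nothing here is confounded. A reader might infer from calcium-guided dosing that the comparison of EPL + cinacalcet with placebo + cinacalcet is invalid. The documents do not support that: dose arises after randomization and lies on the pathway from EPL to PTH. The arms remain comparable, and the A-to-C difference is a valid effect of the whole regimen. This stands.

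A reader might also infer that the EPL arm will receive less cinacalcet, so that the bias must run against EPL. That follows only if EPL lowers serum calcium. The protocol also expects lower urinary calcium excretion, which could push serum calcium upward; the error would then favor false synergy. If calcium does fall, a lower PTH on EPL + cinacalcet at visit C would be a conservative sign of added benefit. The direction has to be left open.

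Further points stand in part:

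- The protocol does not say which calcium draw sets the starting dose. Visit B is an inference from the timing and from the safety bloods taken at every visit. Titration plainly follows randomization.
- The rule is general and the PI may depart from it.
- No B-to-C contrast is specified, and the protocol does not explicitly undertake to tell additive from synergistic.
- The protocol refers to a Detailed Protocol that is not among the documents, so an analysis there cannot be excluded.
- The illustrated PTH shift is mostly below one standard error.

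None of this makes the interaction identifiable. It limits the point to what may be concluded.

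**Conclusion.** The concern holds in a limited form. Exploratory Outcome 2 can support a statement about regimens: PTH at visit C after EPL with calcium-guided cinacalcet against placebo with calcium-guided cinacalcet. It cannot support synergy, or additivity at a common cinacalcet dose, because dose may differ by arm as a result of treatment and no concurrent group is free of cinacalcet from B to C.

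This conclusion rests on the text alone. Its size does not: the gap of about 2 to 41 percentage points depends on assumed calcium means and SDs, and the PTH shift on a further assumed dose response. Neither should be cited as an estimate for this trial.

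The primary A-to-B comparison and its sample size are unaffected. The change is worth making because it alters what the trial may claim, but the consequence is confined to an exploratory outcome.

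**What to change.** 1. In the Protocol's Sample Size section, replace the A-to-B label on Exploratory Outcome 2. There, in Study Drug Interventions and in the SAP, define the outcome as the EPL-versus-placebo difference in PTH change from A to C, described as a comparison of regimens with calcium-guided cinacalcet.
2. Add a table of starting and final cinacalcet dose by arm.
3. Present B to C descriptively, with the caveat that cinacalcet dose may differ by arm in either direction and that continuing EPL effect is not separated from interaction. Adjusting for achieved dose would not restore a randomized comparison.
4. Drop synergy as a conclusion. If additivity is mentioned, say that it is not assessed at a common cinacalcet dose.
5. Reconcile the placebo + amiloride comparator in Anticipated Results with Study Drug Interventions.

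The cost is wording and one table from data on prescribed doses. No dosing rule, visit or sample size changes. The downside is a narrower exploratory claim.

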## **SAMPLE SIZE:**

A sample size of up to 60 total subjects has been chosen using very conservative calculations stemming from our preliminary data (see Detailed Protocol). Therefore, at most there will be 20 subjects per study arm; however, our sample size calculations suggest that we are likely to be adequately powered with a significantly smaller sample size as well. These sample size calculations to achieve sufficient power to observe the primary and secondary outcomes of the study:

- **Primary Outcome:** Change in PTH levels ( $\Delta$ PTH) following randomized drug intervention (**Figure; visits A=>B**).
- **Secondary Outcomes:** Change in serum iCa and markers of bone resorption following randomized drug intervention (**Figure; visits A=>B**).
- Exploratory Outcome 1:  $\Delta$ PTH in response to amiloride therapy (**Figure; visits A=>B**)
- Exploratory Outcome 2:  $\Delta$ PTH in response to combination drug therapy with EPL+ cinacalcet (**Figure; visits A=>B**).
- Exploratory Outcome 3: Correlation of eplerenone-induced  $\Delta$ PTH with MR expression from adenomatous/ hyperplastic parathyroid glands of subjects that undergo parathyroidectomy following study completion.

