  - **Visit C:** 2 weeks +/- 3 days later to assess study outcomes following cinacalcet add-on therapy. Additional safety visits are involved (black diamonds in **Figure**).

- **Study Drug Interventions:** Enrolled subjects will undergo detailed measurements of outcome variables (see detailed outcome variables below) to establish a baseline (**Figure, visit A**). All study visits will be conducted in the morning, following at least 1 hour of monitored supine rest in the Clinical Research Center. Following study visit A, subjects will be randomized to the blinded study drug by the BWH Research Pharmacies. The initial dose of the blinded study drug will be dictated by the subject's blood pressure and the PI's clinical judgment as it relates to reasonable safety. Subjects with blood pressures near the lower range of our safety margin of 105/50 mmHg will receive the lowest dose, and subjects with higher blood pressures (or known hypertension) will receive a higher dose. The initial doses will range from: eplerenone (EPL) 12.5 mg/d to 25 mg/BID, amiloride 1.25 mg/d to 2.5 mg/BID, or placebo. The EPL arm represents the active intervention: a direct MR antagonist. The placebo arm represents a negative control. Since EPL is expected to influence more than just PTH (EPL will also decrease blood pressure and urinary excretion of potassium and calcium) when compared to placebo, the amiloride intervention represents a *second control* to provide insights into the *mechanism* by which EPL may influence PTH. Like EPL, amiloride is a potassium-sparing diuretic, with mild anti-hypertensive and hypocalciuric effects, and will therefore induce similar changes in blood pressure and urinary potassium/calcium excretion. Unlike EPL, amiloride does not directly block the MR. Rather, it blocks epithelial sodium transport channels (ENaC) in the renal distal tubule (and vascular epithelium).

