- *Outcome assessment:* The following measurements will be obtained while fasting at every study visit (**A, B, C**): serum PTH, iCa and total serum calcium, serum phosphate and fibroblast growth factor-23 (FGF-23), 25(OH)D, markers of bone resorption (serum C-telopeptide, urinary N-telopeptide, tartrate-resistant acid phosphatase 5b), markers of bone formation (osteocalcin, bone-specific alkaline phosphatase, P1NP), basic metabolic panel with creatinine, plasma renin activity, serum angiotensin II and ALDO. In addition, 24h urine collections at every study visit, as described above, will be used to measure urinary sodium, potassium, calcium, magnesium, and aldosterone.

Measures of PTH and calcium will be obtained in a standardized fashion after at least 1h of supine rest, at 1h of supine rest, 2h of supine rest, and 3h of supine rest. Subjects will have the option of receiving separate venipunctures at each hour or having an IV placed in their arm for the duration of the study visit which will be used to draw aliquots every hour. The lowest PTH value will be used in analyses.

At study visit A, peripheral blood will be collected for DNA isolation. Although no genetic studies are planned at this time, this DNA will be stored to test future research hypotheses.

Parathyroid tissue will be collected from any subjects that undergo parathyroidectomy (for clinical indications determined by their providers) in the 5 years following their study completion. It is estimated that ~50% of participating subjects may have a surgical parathyroidectomy in the 5 years following their study completion. If the surgery occurs at BWH or MGH, tissue will be collected and flash frozen in liquid nitrogen in the operating room and stored in the BWH pathology

repository, and also formalin fixed in paraffin. Samples will be analyzed for mRNA and protein expression of MR to determine whether there is a correlation of eplerenone-induced  $\Delta$ PTH with MR expression from adenomatous/ hyperplastic parathyroid glands of subjects that undergo parathyroidectomy following study completion. If the surgery occurs at a non-Partners institution, formalin fixed paraffin embedded blocks of tissue will be requested to core a sample and return the block.

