## Statistical Plan

**Analytic Plan, Sample Size and Power:** A sample size of 20 subjects per intervention arm (n=60 total) has been chosen using conservative calculations. The **primary outcome**,  $\Delta$ PTH in response to randomized drug therapy, will be analyzed using a 2-arm ANOVA analysis evaluating the difference between EPL and placebo. A 3-arm ANOVA including the amiloride arm will also be conducted. Sample size calculations are presented in **Figure** using preliminary data from the RAAS-PARC study where the  $\Delta$ PTH= -13 pg/mL was seen with RAAS inhibition in participants with P-HPTH, but also using a more conservative estimate (-9.0 pg/mL) that is 25% lower. It is expected that  $\Delta$ PTH with placebo will range from 0 to +4.57 pg/mL, and calculations have been made to anticipate that amiloride may serve as either a negative control (like placebo) or positive control (like EPL). With these conservative estimates, a sample size of 20 subjects/arm will be sufficient to demonstrate a  $\Delta$ PTH with a type I error of <0.05 and power=80%.

The **secondary outcomes**, change in calcium, will be analyzed in the same fashion as PTH. For calcium, sample size calculations are based on decreases in *total calcium* seen in the RAAS-PARC study ( $\Delta$ Ca= -0.32 mg/dL); treatment with EPL is expected to result in a much greater effect estimate. Thus, using *conservative* estimates of  $\Delta$ Ca= -0.20 to -0.32 mg/dL, a sample size of 20 subjects per intervention arm will be sufficient to achieve 80% power.

**Figure:** Sample size calculations based on  $\Delta$ PTH.

	$\Delta$ PTH	$\Delta$ PTH	$\Delta$ PTH	SD	Sample Size per Arm	
	Placebo	Amiloride	SPIRO		PWR=0.8	PWR=0.9
2-arms	0 pg/mL	-	-9.0 pg/mL	9.4	19	24
	0 pg/mL	-	-13.0 pg/mL	9.4	10	13
	0 pg/mL	0 pg/mL	-9.0 pg/mL	9.4	17	22
	0 pg/mL	0 pg/mL	-13.0 pg/mL	9.4	9	11
	0 pg/mL	-6.5 pg/mL	-13.0 pg/mL	9.4	12	15
	0 pg/mL	-9.0 pg/mL	-13.0 pg/mL	9.4	11	14
3-arms	0 pg/mL	-13.0 pg/mL	-13.0 pg/mL	9.4	9	11

**Figure:** Sample size calculation based on  $\Delta$ Ca.

	$\Delta$ Ca	$\Delta$ Ca	$\Delta$ Ca	SD	Sample Size per Arm	
	Placebo	Amiloride	SPIRO		PWR=0.8	PWR=0.9
	0 mg/dL	0 mg/dL	-0.20 mg/dL	0.21	17	22
	0 mg/dL	0 mg/dL	-0.32 mg/dL	0.21	8	10

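### Does analysing only the lowest of three hourly PTH values, rather than their mean, weaken the primary analysis?

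*Protocol*

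**What the plan says.** The Protocol's outcome assessment paragraph (STUDY PROCEDURES) schedules PTH and calcium "at 1h of supine rest, 2h of supine rest, and 3h of supine rest" at visits A, B and C, and then sets the rule "The lowest PTH value will be used in analyses". The paragraph on study drug interventions says that visits take place in the morning, "following at least 1 hour of monitored supine rest in the Clinical Research Center". It also places the baseline draws before allocation: "Following study visit A, subjects will be randomized to the blinded study drug".

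The primary outcome (Protocol, SAMPLE SIZE) is "Change in PTH levels" from visit A to visit B. Under the SAP's Statistical Plan it "will be analyzed using a 2-arm ANOVA analysis evaluating the difference between EPL and placebo". The sample size is worked out "using preliminary data from the RAAS-PARC study where the" change was -13 pg/mL, and also for a smaller change of -9 pg/mL. The SD is 9.4, and the design is described as adequate "with a type I error of <0.05 and power=80"%. The two-arm row for -9 pg/mL gives 19 per arm at 80% power and 24 at 90%; 20 per arm are planned.

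The text available for review gives no reason for preferring the lowest value and no within-visit SD. It also does not say whether the SD of 9.4 describes a lowest, single or mean value.

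**The concern.** Three blood samples are taken and two are set aside. For independent normal draws, the minimum of three has a variance of 0.559 of the single-draw variance, against 0.333 for the mean. A statistician who sees repeated measurements reduced to an extreme value will suspect two things: that the extreme distorts the comparison, and that power is being lost at no saving. The primary test compares 20 participants per arm, and the conservative scenario clears 80% power only modestly, so avoidable noise in the endpoint would matter. The silence on what the SD of 9.4 measures adds to the doubt, because the planning SD might belong to a different summary of PTH.

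**Working it through.** **1. The plan's own figure.** Inputs from the SAP table: difference 9.0 pg/mL, SD 9.4, alpha 0.05 (two-sided), two arms. A two-arm ANOVA is equivalent to a two-sided t test with noncentrality (9.0/9.4) × √(n/2).
- The smallest n for 80% power is 19 and for 90% is 24, as tabulated. All the other PTH rows and both calcium rows reproduce as well.
- At n = 20, noncentrality is 0.957 × 3.162 = 3.03 and power is 83.9%. At a difference of 13 pg/mL it is 98.9%.

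**2. Validity.** The same function of the three draws is applied at each visit in each arm. With no drug effect, the change in the minimum therefore has the same distribution in every arm. A simulation with 20 per arm, independent draws and a within-visit SD of 4 pg/mL gave a type I error of 0.050 for the lowest value and 0.051 for the mean.

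**3. Possible gain from the mean, under symmetric noise.** Three assumptions are needed, none of them stated in the documents: 9.4 is the SD of change in the lowest value; the within-visit SD of a single draw, w, is 2 to 4 pg/mL; and the drug shifts all three draws equally. Then

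SD of change with the mean = √(9.4² − 2 × (Vmin − Vmean) × w²),

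where Vmin and Vmean are the variances of the minimum and the mean for draws of unit SD. For independent draws and w = 4: √(88.36 − 2 × 0.226 × 16) = √81.13 = 9.01.

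| Correlation of draws | Vmin | Vmean | SD at w = 2 / 4 | Power at w = 2 / 4 | Gain over 83.9% (points) |
|---|---|---|---|---|---|
| Independent | 0.559 | 0.333 | 9.30 / 9.01 | 84.6% / 86.8% | 0.7 / 2.9 |
| AR(1) 0.6 | 0.786 | 0.680 | 9.36 / 9.22 | 84.2% / 85.3% | 0.3 / 1.4 |
| AR(1) 0.8 | 0.886 | 0.831 | 9.38 / 9.31 | 84.1% / 84.6% | 0.2 / 0.7 |

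Over a wider span, w = 1 to 6 with independent draws, the gain runs from 0.2 to 6.5 points. At 13 pg/mL it stays below 0.8 points even at w = 6.

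**4. The same calculation with right-skewed noise.** The minimum is insensitive to occasional high values and the mean is not. With gamma-distributed draws and the same correlation structures:

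| Correlation | Skew at which the gain is zero | Power with the mean at skew 0.5 (w = 2 / 4) | Power with the mean at skew 1.0 (w = 2 / 4) |
|---|---|---|---|
| AR(1) 0.6 | about 0.35 | 83.8% / 83.3% | 83.4% / 81.7% |
| AR(1) 0.8 | about 0.2 | 83.7% / 83.1% | 83.4% / 81.7% |
| Independent | about 0.75 | – | – |

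Beyond the break-even skew, the lowest value is the more precise summary. At skew 1.0, w = 4 and correlated draws, switching to the mean costs 83.9 − 81.7 = 2.2 points.

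**5. A settling trend or isolated spikes.** An early elevation that halves each hour cancels the gain if its average at 1 hour is 1.23w (independent), 0.87w (AR(1) 0.6) or 0.63w (AR(1) 0.8). Spikes of size 5w cancel it when they affect 3.1%, 1.4% or 0.7% of draws respectively. The hour of supine rest before sampling makes a large settling effect less likely but does not address skew or spikes.

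**The case for a change.** The strongest case for the concern is that the gain would be free. The draws are taken anyway, the variance ordering is correct under symmetric noise, and the baseline samples precede randomisation. A blinded look at them could guide the choice: keep the lowest value if PTH clearly falls between 1 and 3 hours or if the draws are strongly right-skewed, and otherwise use the mean.

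The variance arithmetic stands. The safeguard does not. Skew without a trend produces no average fall, so the trend check cannot see it. A criterion of strong skew has no cut-off and would miss the mild skew, 0.2 to 0.35, at which the benefit disappears with correlated draws. Sixty sets of three correlated values could not reliably tell skew of that size from none. The proposal would therefore change a prespecified primary endpoint, conditionally on trial data, for a gain whose sign is unknown.

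A second argument has some force. The expected minimum depends on the number of draws: for independent normal draws it lies 0.85w below the true level with three and 0.56w with two. A missed draw at one visit thus moves that participant's change score by about 0.28w, or 0.6 to 1.1 pg/mL for w = 2 to 4. The text available has no rule for missed draws. This adds noise, but it creates no difference between arms unless missingness differs between them.

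Finally, a stated reason for the lowest value and the definition behind 9.4 would be useful to a reader. The Protocol refers to a Detailed Protocol for its preliminary data, and part of the SAP was not available, so their absence here cannot be counted against the plan. Supplying them, or adding the mean as a sensitivity analysis, would leave the planned primary test and its sample size unchanged.

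**Conclusion.** The concern does not hold. The lowest-value rule is prespecified and identical across visits and arms, and it leaves type I error at its nominal level. The stated sample size reproduces, and power at 20 per arm is 83.9%, above the 80% target, provided that 9.4 is the SD of the change actually analysed. The alternative offers about 0.2 to 1.4 points with correlated draws and 0.7 to 2.9 with independent ones, if w is 2 to 4 pg/mL and the noise is symmetric. Under modest right skew it offers nothing or a loss, up to about 2 points in the cases examined. The documents contain no within-visit data that would settle which condition applies. Reasonable statisticians could choose either summary, and the plan's choice is sound as it stands.
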